9.7 Dose Modification

No dose modifications are allowed. Treatment may be interrupted as outlined in Section 9.8. If any unacceptable toxicity arises in the opinion of the investigator, individual subjects may discontinue dosing. The Vertex medical monitor must be notified immediately.

9.8 Study Drug Interruption

Study drug may be interrupted for safety concerns by the investigator. The Vertex medical monitor should be notified of an interruption of study drug and of the resumption of study drug after such interruption.

9.9 Removal of Subjects

Subjects may withdraw from the study at any time at their own request. Subjects may be withdrawn from study drug treatment at any time at the discretion of the investigator or Vertex

for safety, behavior, noncompliance with study procedures, or administrative reasons. A subject who withdraws from study drug treatment will continue to be followed unless the subject withdraws consent.

Subjects who discontinue study treatment early should complete the ETT and SFUV, as noted in Sections 9.1.2.2 and 9.1.2.3.

If a subject does not return for a scheduled visit, reasonable effort will be made to contact the subject. In any circumstance, reasonable effort will be made to document subject outcome. The investigator will inquire about the reason for withdrawal, request that the subject return all unused investigational product(s), request that the subject return for a SFUV, if applicable (see Section 9.1.2.3), and follow up with the subject regarding any unresolved AEs.

If a subject withdraws consent for the study, no further assessments will be performed. Vertex may retain and continue using the study data and samples after the study ends and may use the samples and information in the development of the study compound, for other drugs and diagnostics, in publications and presentations, and for education purposes. If a subject withdraws from the study, the study data and samples collected will remain part of the study. A subject will not be able to request the withdrawal of his/her information from the study data. A subject may request destruction of the samples collected from him/her during the study as long as those samples can be identified as his/her samples.

9.10 Replacement of Subjects

Subjects who withdraw or are withdrawn for nonsafety reasons during the study drug treatment period(s) may be replaced at Vertex's discretion.

10 STUDY DRUG INFORMATION AND MANAGEMENT

10.1 Preparation and Dispensing

Study drug may be dispensed only under the supervision of the investigator or an authorized designee and only for administration to the study subjects.

10.2 Packaging and Labeling

Vertex will supply the 15-mg VX-147 tablets. Study drug labeling will be in compliance with applicable local and national regulations. Additional details about packaging, labeling, and dispensing for VX-147 will be in the Pharmacy Manual.

10.3 Study Drug Supply, Storage, and Handling

The investigator, or an authorized designee (e.g., a licensed pharmacist), will ensure that all investigational product is stored in a secured area, under recommended storage conditions, and in accordance with applicable regulatory requirements. To ensure adequate records, all study drugs will be accounted for in the drug accountability forms as instructed by Vertex.

Detailed instructions regarding the storage, handling, and dispensation of the study drug will be provided in the Pharmacy Manual.

Table 10-1 Study Drug

	Dosing Form/		
Drug Name	Route	Dosage	How Supplied
	Tablet/		
VX-147	oral	15-mg	Supplied as 15-mg tablets
	Tablet/		Supplied as 3 × 15-mg
VX-147	oral	45-mg	tablets

10.4 Drug Accountability

The pharmacist or designated study site staff will maintain information about the dates and amounts of (1) study drug received; (2) study drug dispensed to the subjects; and (3) study drug returned by the subjects. A central pharmacy will be used. Subjects will be instructed to return all used and unused materials associated with the study drug to the home health nurse or site. These materials will be retained at the site or central pharmacy according to instructions provided by Vertex or its designee. The study monitor will review study drug records and inventory throughout the study. If a site or central pharmacy uses a site-specific drug accountability system and/or process, including processes associated with the destruction of returned materials, the process must be documented and approved by Vertex. The study monitor must review the drug accountability documentation on a regular basis. The study monitor will promptly communicate to Vertex any discrepancies he/she is unable to resolve with the site.

10.5 Disposal, Return, or Retention of Unused Drug

The study site staff or pharmacy personnel will retain all materials returned by the subjects until the study monitor has performed drug accountability. The investigator will ensure that the materials are destroyed in compliance with applicable environmental regulations, institutional policy, and any special instructions provided by Vertex. Destruction will be adequately documented.

10.6 Compliance

To ensure treatment compliance, the investigator or designee will supervise all study drug dosing that occurs at the site or in the subject's home at required study visits. At each visit, site personnel/home health care nurses will review that the subject is compliant with study drug dosing and remind the subject of study drug dosing requirements. Compliance will also be assessed by ongoing study drug count.

If a subject demonstrates continued noncompliance of study drug dosing despite educational efforts, the investigator should consider discontinuing the subject from the study

10.7 Blinding and Unblinding

This is an open-label study.

11 ASSESSMENTS

The schedule of assessments is shown in Table 3-1 through Table 3-3.

11.1 Subject and Disease Characteristics

Subject and disease characteristics include the following: demographics, medical history, height, and weight.

Medical history will be elicited from each subject and extracted from medical records during screening. Based on the medical history, the subject will be assessed for any disqualifying medical conditions as specified in the inclusion and exclusion criteria. The medical history will include a complete review of systems, past medical and surgical histories, and any allergies.

Height and weight will be measured with shoes off with light weight clothing (no outerwear). BMI will be calculated from weight and height.

11.2 Pharmacokinetics

11.2.1 Blood Sampling

Blood samples will be collected to determine plasma concentrations of VX-147. Metabolites of VX-147 may be analyzed, if necessary. These samples may also be used for further evaluation of the bioanalytical method, evaluation of unbound concentration of VX-147, and for exploratory analyses that provide information on the metabolic pathways used by or affected by VX-147; these results may not be included in the clinical study report.

All efforts will be made to obtain the PK samples at the exact nominal time relative to dosing. Acceptable windows for sampling times are shown in Table 11-1. Samples collected outside of these acceptable windows will be considered protocol deviations.

Table 11-1 Acceptable Pharmacokinetic Sampling Windows

Sampling Time	Time From Scheduled Sampling Allowed		
Predose	Up to 60 minutes before dose		
From 0.25 up to ≤4 hours after study drug dosing	\pm 15 minutes		
> 4 hours after study drug dosing	± 120 minutes		
48 hours after study drug dosing	± 180 minutes		

For each visit with a PK blood draw, a record of study drug administration will be collected. The collection date and exact time that each PK blood sample is drawn will also be recorded.

Samples from the PK sampling will be kept frozen by Vertex or its designee until all analyses have been completed and then disposed of according to Vertex or designee standard operating procedures.

11.2.2 Processing and Handling of Pharmacokinetic Samples

Detailed procedures for the collection of samples and further procedures for processing and handling of samples for PK analysis will be in a separate document.

11.2.3 Bioanalysis

Samples will be analyzed using a validated analytical method in compliance with Vertex or designee standard operating procedures. A description of the assay and validation data will be provided in separate reports.

11.3 Urine Sampling for UPCR, UACR, and Safety Laboratory Panel

Urine will be collected from the first morning void (predose) for use in efficacy and safety analyses. Efficacy analyses will include UPCR (primary endpoint) and UACR (exploratory endpoint), as calculated from protein, albumin, and creatinine measured in the urine. Safety assessments will include the urine laboratory parameters in Section 11.6.2. During the Screening, Week 5, Week 9, and Week 13 Visits, when 3 samples are collected on 3 separate days within a 7-day period, the third sample collected will be used for the safety laboratory and biomarker assessments; all 3 samples will be used for UPCR and UACR.

If the subject does not remember to collect their first morning void on the scheduled visit day, the subject may provide the sample on another day within the visit window.

Details about the collection and processing of urine samples will be provided in the Laboratory Manual.

11.4 APOL1 Genotyping

A blood sample will be collected for determining APOL1 genotype during screening. This sample is not required if a genotype result is available from a previous Vertex study using a Vertex-approved clinical study assay.

The results of the genotyping test will be provided to the investigator. The investigator will inform the subject of the *APOL1* genotype. Vertex will ensure that subjects can obtain the services of a genetic counselor, if desired. The site will be responsible for managing the corresponding logistics.

11.5 Exploratory Assessments

These data will be used for internal exploratory purposes. Detailed procedures for the collection of blood and urine, as well as additional procedures for processing and handling samples, will be provided in a separate document.

11.5.1 Blood Biomarker Samples

Blood samples will be collected for potential exploratory evaluation of correlations between blood markers (e.g., post-translational APOL1 protein modification, peptides, lipids, endogenous metabolites, etc.) with PK and AEs observed in the study. The samples may also be used for the evaluation of safety biomarkers.

11.5.2 Urine Biomarker Samples

Urine samples will be collected from the first morning void for potential exploratory evaluation of correlations between urine biomarkers (e.g., exosomes) with PK treatment response, and AEs observed in the study. At visits where triplicate urine samples are collected, only the third urine sample will be used for urine biomarker analysis. Additional details will be provided in the Laboratory Manual.

11.5.3 SF-36

Subjects will complete the SF-36 in their native language (if validated translations are available) before all other study assessments at each scheduled time point. If there is no validated translation available in the subject's native language, the subject will not complete the questionnaire. The questionnaire provides information about functional health and wellbeing, as well as 2 psychometrically based physical and mental health summary measures.

11.6 Safety

Safety evaluations will include AEs, clinical laboratory assessments, clinical evaluation of vital signs, ECGs, and physical examinations (PEs).

11.6.1 Adverse Events

All AEs will be assessed, documented, and reported in accordance with ICH GCP Guidelines. Section 13.1 outlines the definitions, collection periods, criteria, and procedures for documenting, grading, and reporting AEs. A separate document that details AE CRF completion guidelines for investigators as well as training will be provided.

11.6.2 Clinical Laboratory Assessments

The safety laboratory test panels are shown in Table 11-2. For purposes of study conduct, blood and urine samples will be analyzed at a central laboratory, with the exception of urine pregnancy tests and if there are extenuating circumstances due to COVID-19, as described below.

Urine samples for safety laboratory assessments may be collected at the same time as the urine samples for efficacy and biomarker assessments (See Section 11.3). Refer to sample handling guidelines to ensure that each sample collected is submitted appropriately to the lab for analysis at each visit. At the Screening, Week 5, Week 9, and Week 13 Visits, only the third urine sample will be used for safety urinalysis and biomarker assessments; urine protein, creatinine, and albumin will be assessed for all 3 samples collected during this visit.

On days when overnight fasts are required (see Table 3-2 and Table 3-3), subjects will abstain from food and beverages for 8 hours before the start of the visit. During this period, water may be consumed up to 1 hour before study drug administration.

Local laboratories may be used at the discretion of the local investigator for management of urgent medical issues. If a local laboratory test value is found to be abnormal and clinically significant, it will be verified by the central laboratory as soon as possible after the investigator becomes aware of the abnormal result. If it is not possible to send a timely specimen to the central laboratory (e.g., the subject was hospitalized elsewhere), the investigator may base the assessment of an AE on the local laboratory value. Laboratory test results that are abnormal and considered clinically significant will be reported as AEs (see Section 13.1).

The central laboratory should be used for all assessments when possible, and Vertex should be notified if a local laboratory is to be used. If the subject is unable to have a clinic or home health visit due to extenuating circumstance of the COVID-19 global pandemic, local laboratories may be used after Day 1 for blood safety samples. When local labs are used for blood safety sample collection, the site will obtain the results from the local lab and ensure data are captured in the electronic data capture (EDC) per Section 13.5. Local labs may not be used for screening assessments.

Table 11-2	Safety	Laboratory	Test Pa	anels
-------------------	--------	------------	---------	-------

Serum Chemistry	Hematology	Urinalysis ^a	
Glucose	Hemoglobin	Leukocyte esterase	
Blood urea nitrogen ^b	Hematocrit	Nitrite	
Creatinine	Erythrocytes	Urine protein ^c	
Creatine kinase	Mean corpuscular volume	Urine creatinine ^c	
Sodium	Platelets	Urine albumin ^c	
Potassium	Reticulocytes	Urine blood	
Calcium	Leukocytes		
Chloride	Differential (absolute and percent):		
Magnesium	Eosinophils	Urine ketones	
Bicarbonate	Basophils	Urine glucose	
Phosphate	Neutrophils	Urobilinogen	
Total bilirubin, direct bilirubin	Lymphocytes	Urine pH	
Alkaline phosphatase	Monocytes	Specific gravity	
Aspartate transaminase	Blood smear ^e		
Alanine transaminase	Coagulation		
Amylase	Activated partial thromboplastin time		
Lipase	Prothrombin time		
Gamma-glutamyl transferase	Prothrombin time International		
Protein	Normalized Ratio		
Albumin			
Cholesterol ^d			
Triglycerides ^d			
Low-density lipoprotein-direct ^d			
High-density lipoprotein ^d			

^a For the Day 1 predose sample, microscopic examination of urine will be done, and results will be provided for leukocytes, erythrocytes, crystals, bacteria, and casts.

Additional Tests at Screening: The following additional tests will be performed during screening to assess eligibility:

- *Serum beta-human chorionic gonadotropin (\beta-hCG) for all subjects*: Serum samples will be analyzed for β -hCG at the central laboratory.
- Follicle-stimulating Hormone (Screening Period only): Blood sample for FSH will be measured for any suspected postmenopausal female with at least 12 months of continuous spontaneous amenorrhea. Serum FSH levels must be within the postmenopausal reference range of the performing laboratory to be considered postmenopausal.
- *APOL1*: A blood sample will be collected to determine *APOL1* genotype, if required per Table 3-1.
- *HIV-1 and HIV-2 antibodies:* A blood sample will be collected for serology.
- Hepatitis B surface antigen: A blood sample will be collected for serology.

b If blood urea nitrogen cannot be measured, urea may be substituted.

eGFR will be calculated using the CKD-EPI equation, and AKI will be determined using KDIGO criteria. 24 Urine protein, creatinine, and albumin measurements will be used for efficacy and safety.

d Lipid profile will only be measured at the visits with fasting: Day 1, Week 3, Week 13, ETT, and SFUV.

^e A blood smear will be collected on Day 1, Week 13, and the ETT Visit.

• *Hepatitis C Virus (HCV):* A blood sample will be collected for serology and nucleic acid testing. If the antibody test is positive, a nucleic acid test will be done.

Algorithm for assessing out of range laboratory values at Screening:

If one or more lab values NOT specified in the eligibility criteria (Section 8) are outside the normal range, the following choices are available:

- The subject may be excluded.
- The subject may be included if the lab value(s) are not clinically significant, as determined by the principal investigator (PI).
- The subject may be included if the lab abnormality is consistent with a pre-existing medical condition that is NOT excluded per protocol.
- Repeat the test for the individual lab assessment per the guidance in Section 9.1.1.1.

Pregnancy Testing for Female Subjects of Childbearing Potential (Section 11.6.5):

• Urine pregnancy tests will either be performed and analyzed at the site or, when there is a home health visit, at home using a home kit provided by the site/home health nurse. The urine pregnancy test on Day 1 must be negative before the first dose of study drug. Additional pregnancy tests may be required according to local regulations and/or requirements.

If a urine pregnancy test is positive, all study drug dosing will stop, and the pregnancy will be confirmed with a serum β -hCG test. If pregnancy is confirmed, the procedures outlined in Section 11.6.5.2 will be followed.

Additional Evaluations: Additional clinical laboratory evaluations will be performed at other times if judged to be clinically appropriate.

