8.1 Inclusion Criteria

The following criteria are applicable for Cohort 1 and Cohort 2:

- 1. Willing to sign and date an informed consent form (ICF).
- 2. Willing and able to comply with scheduled visits, treatment plan, study restrictions (Section 9.59.4), laboratory tests, contraceptive guidelines (Section 11.6.5), and other study procedures.
- 3. An *APOL1* genotype of *G1/G1*, *G2/G2*, or *G1/G2* obtained with a Vertex-approved clinical study assay.
- 4. Between the ages of 18 and 65 years, inclusive.
- 5. Body mass index (BMI) of 18.0 to 40.0 kg/m², inclusive, and a total body weight >50 kg.
- 6. FSGS diagnosed by kidney biopsy, with the exception of the tip variant, as confirmed through the eligibility review process.
- 7. There should be no plan to start, stop, or modify dosing for an angiotensin converting enzyme (ACE) inhibitor, angiotensin receptor blocker (ARB), neprilysin inhibitor, sodium-glucose co-transporter-2 (SGLT2) inhibitor, renin inhibitor, systemic corticosteroids, tacrolimus, mycophenolate, or cyclosporine from 28 days before Screening through the Follow-up Period.
- 8. Subjects who are on low-dose corticosteroids (prednisone ≤ 10 mg per day or prednisone equivalent) or on an allowed immunosuppressant (i.e. tacrolimus, mycophenolate, or cyclosporine) must be on a stable dose for 28 days before screening.
- 9. Estimated glomerular filtration rate (eGFR) ≥30 mL/min/1.73 m² (±10%) based on the Chronic Kidney Disease Epidemiology Collaboration (CKD-EPI) equation. ^{13, 14}

10. Subjects with eGFR \geq 30 (\pm 10%) to \leq 40 mL/min/1.73 m² must have tubulointerstitial fibrosis \leq 50% or described as no, mild, or moderate on their kidney biopsy.

The following criterion is applicable for Cohort 1:

11. A UPCR ratio of ≥ 3 g/g ($\pm 10\%$) and ≤ 10 g/g in the first morning void on 3 measurements collected on at least 3 separate days within a 7-day period, during the Screening Period. The average of the 3 measurements must meet this criterion.

The following criterion is applicable for Cohort 2:

12. A UPCR ratio of ≥0.8 g/g (±10%) and <2.7 g/g in the first morning void on 3 measurements collected on at least 3 separate days within a 7-day period, during the Screening Period. The average of the 3 measurements must meet this criterion.

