9.2.2 Demographics and Baseline Characteristics

Demographics and baseline characteristics will be summarized based on the FAS by cohort and overall.

Demographic data will include the following:

- Age (in years)
- Sex (female and male)
- Ethnicity (Hispanic or Latino, not Hispanic or Latino, and not collected per local regulations)
- Race (White, Black or African American, Asian, American Indian or Alaska Native, Native Hawaiian or other Pacific Islander, Other, Not collected per local regulations, Other, and Multiracial [if more than 2 races reported from a subject])

Baseline and disease characteristics will include the following:

- Weight (kg)
- Height (cm)
- BMI (kg/m²)
- *APOL1* genotype (*G1/G1*, *G2/G2*, or *G1/G2*)
- UPCR (g/g)
- UACR (g/g)
- eGFR (mL/min/1.73 m²)
- eGFR (mL/min/1.73 m²) category (<40, ≥40 to <60, ≥60)
- Systolic blood pressure (mmHg)
- Diastolic blood pressure (mmHg)
- Prior medication of any systemic corticosteroid (Yes, No)
- Prior medication of any immunosuppressants (Yes, No)

- Prior medication of any angiotensin converting enzyme (ACE) inhibitor (Yes, No)
- Prior medication of any angiotensin II receptor blocker (ARB) (Yes, No)
- Prior medication of any neprilysin inhibitor (Yes, No)
- Prior medication of any sodium-glucose cotransporter-2 (SGLT2) inhibitor (Yes, No)
- Prior medication of any diuretic (Yes, No)
- Prior medication of any renin inhibitor (Yes, No)
- Prior medication of any statin (Yes, No)
- Medical history of diabetes (Yes, No)

In addition, data listings will also be provided for:

- Informed consent
- Inclusion/Exclusion criteria violation for subjects with any such violations

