9.4.2 Clinical Laboratory

All statistical analyses of laboratory values will be performed using SI units. For treatment-emergent laboratory measurements, the observed values and change from baseline values of the continuous hematology, chemistry, and coagulation results will be summarized at each visit.

The number and percentage of subjects with selected test values meeting at least 1 threshold analysis criterion event during the TE period will be summarized. The threshold analysis criterion shift from baseline will also be summarized for selected laboratory test values. The threshold analysis criteria are provided in [Appendix D](#).

Results of urinalysis and the urine/serum pregnancy test will be in individual subject data listings only.

In addition, a listing of individual subject hematology, chemistry, and coagulation values outside the normal reference ranges will be provided. This listing will include data from both scheduled and unscheduled visits.

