Appendix D: Criteria for Threshold Analysis

Table 12-3 Threshold Analysis Criteria for Laboratory Tests (as applicable)

Parameter	Threshold Analysis	Comments
Clinical Chemistry		
ALT	>ULN - ≤3xULN >3x - ≤5xULN >5x - ≤8xULN >8x - ≤20.0xULN >20.0xULN	FDA DILI Guidance Jul 2009.
AST	>ULN - ≤3xULN >3x - ≤5xULN >5x - ≤8xULN >8x - ≤20.0xULN >20.0xULN	FDA DILI Guidance Jul 2009.
ALT or AST	(ALT>ULN - ≤ 3xULN) or (AST>ULN - ≤3xULN) (ALT>3x - ≤5xULN) or (AST>3x - ≤5xULN) (ALT>5x - ≤8xULN) or (AST>5x - ≤8xULN) (ALT>8x - ≤20xULN) or (AST>8x - ≤20xULN) ALT>20xULN or AST>20xULN	FDA DILI Guidance Jul 2009.
Alkaline Phosphatase	>ULN - ≤1.5xULN >1.5 - ≤2.5xULN >2.5 - ≤5.0xULN >5.0 - ≤20.0xULN >20.0xULN	FDA DILI Guidance Jul 2009.
Total Bilirubin	>ULN - ≤1.5xULN >1.5 - ≤2xULN >2 - ≤3xULN >3 - ≤10xULN >10xULN	FDA DILI Guidance Jul 2009.
Direct Bilirubin	>ULN - ≤1.5xULN >1.5 - ≤2xULN >2 - ≤3xULN >3 - ≤10xULN >10xULN	FDA DILI Guidance Jul 2009.
ALT and Total Bilirubin	ALT>3xULN and TBILI>2xULN	FDA DILI Guidance Jul 2009.
AST and Total Bilirubin	AST>3xULN and TBILI>2xULN	FDA DILI Guidance Jul 2009.
(ALT or AST) and Total Bilirubin	(ALT>3xULN or AST>3xULN) and TBILI>2xULN	FDA DILI Guidance Jul 2009.

Table 12-3 Threshold Analysis Criteria for Laboratory Tests (as applicable)

Parameter	Threshold Analysis	Comments
GGT	>ULN - ≤2.5xULN >2.5 - ≤5.0xULN >5.0 - ≤20.0xULN >20.0xULN	CTCAE grade 1-4
Albumin	<LLN - ≥30 g/L <30 - ≥20 g/L <20 g/L	CTCAE grade 1-3
Amylase	>1x - ≤1.5xULN >1.5x - ≤2xULN >2x - ≤5xULN >5xULN	Criteria based upon CTCAE
Creatinine	>ULN - ≤1.5xULN >1.5 - ≤3.0xULN >3.0 - ≤6.0xULN >6.0xULN	CTCAE grades 1-4
Lipase	>ULN - ≤1.5xULN >1.5x - ≤2xULN >2x - ≤5xULN >5xULN	Criteria based upon CTCAE
Total protein	<LLN >ULN	No CTCAE
Creatine kinase	>ULN - ≤2.5xULN >2.5 - ≤5xULN >5 - ≤10xULN >10xULN	CTCAE grades 1-4
Cholesterol	<5.18 mmol/L ≥5.18 - <6.22 mmol/L ≥6.22 mmol/L	ATP III guideline
Triglycerides	<1.70 mmol/L ≥1.70 - <2.26 mmol/L ≥2.26 - <5.65 mmol/L ≥5.65 mmol/L	ATP III guideline
HDL Cholesterol	<1.04 mmol/L ≥1.04 - <1.55 mmol/L ≥1.55 mmol/L	ATP III guideline
LDL Cholesterol	<2.59 mmol/L ≥2.59 - <3.37 mmol/L ≥3.37 - <4.14 mmol/L ≥4.14 - <4.92 mmol/L ≥4.92 mmol/L	ATP III guideline
Hematology		

Table 12-3 Threshold Analysis Criteria for Laboratory Tests (as applicable)

Parameter	Threshold Analysis	Comments
Hemoglobin	Hgb decreased (anemia) <LLN - ≥ 100 g/L <100 - ≥ 80 g/L <80 g/L	CTCAE grade 1-3

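### The protocol says eGFR will be calculated and AKI determined by KDIGO criteria, but the SAP plans no post-baseline eGFR or AKI output and grades creatinine only in multiples of ULN

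*Protocol*

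**What the plan says.** **Protocol V6.** The note to Table 11-2 (Section 11.6.2) reads "eGFR will be calculated using the CKD-EPI equation, and AKI will be determined using KDIGO criteria". Section 12.3.4.2 plans by-visit summaries of continuous chemistry values and a threshold analysis with a shift from baseline. It leaves the threshold criteria to the SAP and names neither eGFR nor AKI. Inclusion criterion 9 (Section 8.1) admits subjects at eGFR of at least 30 mL/min/1.73 m², with a 10% tolerance.

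**SAP.**
- eGFR appears in the cohort description (7.1) and among the baseline characteristics (9.2.2). AKI and KDIGO do not appear. Section 3.1 records no modification to the protocol.
- For laboratory data, 9.4.2 plans that "the observed values and change from baseline values of the continuous hematology, chemistry, and coagulation results will be summarized at each visit". It adds that "The threshold analysis criterion shift from baseline will also be summarized for selected laboratory test values", without naming the tests.
- It also plans that "a listing of individual subject hematology, chemistry, and coagulation values outside the normal reference ranges will be provided".
- The creatinine row of Table 12-3 (Appendix D) is ">ULN - ≤1.5xULN >1.5 - ≤3.0xULN >3.0 - ≤6.0xULN >6.0xULN".
- For ECG, blood pressure and weight, Tables 12-4 and 12-5 do include change-from-baseline criteria.

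**The concern.** Safety is a secondary objective, the trial has no control arm, and the protocol's introduction describes these patients as at risk of rapid loss of kidney function. Change within the subject is therefore the main interpretable renal signal.

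Bands fixed to ULN suit subjects who start in the normal range. They fit less well when the disease itself has already raised creatinine:
- The threshold count picks up subjects whose creatinine has not moved.
- The shift table, if creatinine is in it at all, records a change only when a subject crosses a band edge.

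The two measures that would answer the question directly, eGFR change and AKI by a stated criterion, are named in the protocol but have no output in the SAP. Interim analyses reuse SAP 9.4 and inherit the gap.

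**Working it through.** The plan gives no figure of its own on this point. The check has four steps.

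**1. Largest rise inside one band** (limits from SAP Table 12-3): ratio = upper limit / lower limit.
- >1 to 1.5 x ULN: 1.5 / 1.0 = 1.5, so just under 1.5-fold.
- >1.5 to 3.0 x ULN: 3.0 / 1.5 = 2.0, so just under 2-fold.
- Example: 2.9 / 1.6 = 1.81-fold, with start and end both in the >1.5 to 3.0 band.

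**2. What that means for eGFR.** The documents name CKD-EPI but do not print it. Assumption: eGFR is proportional to creatinine^(-b), with b from 1.0 (simple inverse) to 1.209 (taken as the CKD-EPI 2009 exponent at raised creatinine). Fall = 1 - ratio^(-b).

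| Creatinine ratio | Fall, b = 1.0 | Fall, b = 1.209 |
|---|---|---|
| 1.5 | 33.3% | 38.8% |
| 1.81 | 45% | 51% |
| 2.0 | 50.0% | 56.7% |

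**3. Where subjects start in a band.** Assumptions: CKD-EPI 2009, age 40, both sexes, with and without the race term; ULN 1.2 or 1.3 mg/dL for men and 0.9, 1.0 or 1.1 mg/dL for women. That gives ten settings. For each, creatinine is raised to the top of its starting band.

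| Baseline eGFR | Starting creatinine (x ULN) | Largest eGFR fall with no band change |
|---|---|---|
| 30 | 1.84 to 2.54 | 18% to 45% |
| 40 | 1.45 to 2.00 | 39% to 55% in nine settings, 4% in one |
| 60 | 1.04 to 1.43 | 5% to 36% |

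Example: for a man with ULN 1.2 and no race term, creatinine of 2.02 mg/dL (eGFR 40) can reach 3.60 mg/dL (eGFR 20) with no shift. The 4% case is a woman with ULN 1.1 and no race term, who starts just below a band edge. At all three baselines every setting starts above ULN, so a subject who does not change still meets a threshold criterion.

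**4. Which bands matter at entry.** The floor is 30 x 0.9 = 27. Going from eGFR 30 to 27 multiplies creatinine by (30/27)^(1/1.209) = 1.091. The starting range becomes 1.84 x 1.091 = 2.0 to 2.54 x 1.091 = 2.8 x ULN. At age 40, entry above 3.0 x ULN is not reached in any of the ten settings.

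**The case against.** The strongest reply is that the SAP already shows within-subject change in creatinine.
- By-visit summaries cover change from baseline, and SAP 9.1 defines the descriptive statistics to include minimum and maximum. In a cohort of about 10, one large rise would set the maximum.
- Out-of-range values are listed by subject, from scheduled and unscheduled visits, and with about 20 subjects the listing can be read.
- Protocol 13.1.1.2 sends clinically significant worsening from baseline to adverse events.
- The protocol note says AKI is determined, not tabulated, and 12.3.4.2 asks for no AKI analysis.
- No laboratory test in Table 12-3 has a baseline-relative criterion, so creatinine was not singled out, and its bands follow CTCAE grades.

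Most of this stands. A reader might infer that renal decline would be missing from the report, or that the SAP drops an analysis the protocol required. The documents support neither reading.

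Three limits remain:
- A maximum at a visit shows that someone rose, not how many did. The visit value is the one closest to the target day (Appendix A), so an unscheduled peak can drop out. SAP 9.1 mentions maximum change over the TE Period only as a rule for using unscheduled data; 9.4.2 plans no such laboratory table.
- A listing in which chronically raised values are all out of range does not flag who worsened.
- Adverse event reporting depends on the investigator's judgement of clinical significance, whereas the protocol names a defined criterion for AKI.

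**Conclusion.** The point holds as a gap between the protocol note and the SAP outputs, and as a poor fit of ULN-only bands to this population. No planned table counts subjects by worsening from their own baseline value. The shift table can count only those who cross a ULN-multiple edge, and creatinine is not named among its tests.

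The band arithmetic needs no assumption: just under 1.5-fold and just under 2-fold can pass with no shift. The eGFR equivalents rest on the assumed exponent and ULNs. Two-fold is a maximum, not a typical value; the hidden amount depends on where in the band the subject starts and can be as small as 4%. A reader might extend the point to the >3.0 to 6.0 band, but the eGFR entry floor makes that an unlikely starting place.

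This is a worthwhile, inexpensive improvement to a descriptive safety analysis. It does not affect the primary endpoint.

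**What to change.** In SAP 9.4.2 add, by cohort and overall:
1. eGFR observed value and change from baseline at each visit.
2. Each subject's maximum ratio of creatinine to own baseline during the TE Period, using scheduled and unscheduled values.
3. A count and listing of subjects meeting the KDIGO AKI criteria that the protocol already cites, with the reference value and the handling of scheduled and unscheduled measurements written out.

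Name creatinine among the tests in the threshold shift table. Keep the ULN-band counts beside these outputs.

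The cost is SAP wording and a few extra descriptive tables. Serum chemistry is already drawn at every Part A visit and at the Safety Follow-up Visit, so no samples or visits are added.
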